10.0 CRITERIA FOR EVALUATION AND ENDPOINT ANALYSIS

- 10.1 Measurability of Lesions
 - a. Measurable disease: Measurable disease is defined differently for lymph nodes compared with other disease and will be addressed in a separate section below.
 - Lesions that can be accurately measured in at least one dimension (longest diameter to be recorded) as ≥ 2.0 cm by chest x-ray, by ≥ 1.0 cm with CT or MRI scans, or ≥ 1.0 cm with calipers by clinical exam. All tumor measurements must be recorded in decimal fractions of centimeters (or millimeters).

The defined measurability of lesions on CT scan is based on the assumption that CT slice thickness is 0.5 cm or less. If CT scans have slice thickness greater than 0.5 cm, the minimum size for a measurable lesion should be twice the slice thickness.

- 2. Malignant lymph nodes are to be considered pathologically enlarged and measurable if it measures ≥ 1.5 cm in **SHORT AXIS** (greatest diameter perpendicular to the long axis of the lymph node) when assessed by scan (CT scan slice recommended being no greater than 0.5 cm).
- b. Non-measurable disease: All other lesions (or sites of disease), including small lesions (longest diameter < 1.0 cm or pathologic lymph nodes with ≥ 1.0 cm to < 1.5 cm short axis), are considered non-measurable disease. Bone lesions, leptomeningeal disease, ascites, pleural/pericardial effusions, lymphangitis cutis/pulmonitis, inflammatory breast disease, and abdominal masses (not followed by CT or MRI), are considered non-measurable as are previously radiated lesions that have not progressed.

c. Notes on measurability

- 1. For CT and MRIs, the same type of scanner should be used and the image acquisition protocol should be followed as closely as possible to prior scans. Body scans should by performed with breath-hold scanning techniques, if possible.
 - PET-CT: At present, the low dose or attenuation correction CT portion of a PET-CT is not always of optimal diagnostic CT quality for use with RECIST measurements. However, if the site can document that the CT performed as part of a PET-CT is of identical diagnostic quality to a diagnostic CT, then the CT portion of the PET-CT can be used for RECIST measurements and can be used interchangeably with conventional CT.
- 3. Ultrasound: Ultrasound is not useful in assessment of lesion size and should not be used as a method of measurement.
- 4. Cystic lesions that meet the criteria for radiographically defined simple cysts should not be considered as malignant lesions (neither measurable nor non-measurable) since they are, by definition simple cysts.
- 5. If a target lesion becomes very small some radiologists indicate that it is too small to measure. If the lesion is actually still present, a default

measurement of 0.5 cm should be applied. If the radiologist believes the lesion has gone, a default measurement of 0.0cm should be recorded.

10.2 Objective Status at Each Disease Evaluation

Objective Status is to be recorded at each evaluation. All measurable lesions up to a maximum of 2 lesions per organ 5 lesions in total, representative of all involved organs, should be identified as target lesions at baseline. All other lesions (or sites of disease) including any measurable lesions over and above the 5 target lesions should be identified as non-target lesions. Measurements must be provided for target measurable lesions, while presence or absence must be noted for non-target measurable and non-measurable disease.

For studies that use disease progression as an endpoint, whole body scanning at specific intervals is necessary to determine that progression is NOT present outside of the "target" areas. Therefore, in these studies it is not acceptable to image only the "target" areas of the body in follow-up scans. For study-specific imaging requirements, see the Study Calendar in Section 9.0.

- a. Complete Response (CR): Complete disappearance of all target and non-target lesions (with the exception of lymph nodes mentioned below). No new lesions. No disease related symptoms. Any lymph nodes (whether target or non-target) must have reduction in short axis to < 1.0 cm. All disease must be assessed using the same technique as baseline.
- b. Partial Response (PR): Applies only to patients with at least one measurable lesion. Greater than or equal to 30% decrease under baseline of the sum of appropriate diameters of all target measurable lesions. No unequivocal progression of non-measurable disease. No new lesions. All target measurable lesions must be assessed using the same techniques as baseline.
- c. Stable: Does not qualify for CR, PR, Progression or Symptomatic Deterioration. All target measurable lesions must be assessed using the same techniques as baseline.
- d. Progression: One or more of the following must occur: 20% increase in the sum of appropriate diameters of target measurable lesions over smallest sum observed (over baseline if no decrease during therapy) using the same techniques as baseline, as well as an absolute increase of at least 0.5 cm. Unequivocal progression of non-measurable disease in the opinion of the treating physician (an explanation must be provided). Appearance of any new lesion/site. Death due to disease without prior documentation of progression and without symptomatic deterioration (see Section 10.2e).

Notes regarding new lesions: FDG-PET imaging can complement regular scans in identifying new lesions according to the following algorithm.

- 1. Negative FDG-PET at baseline, with a positive FDG-PET at follow-up is a sign of progression based on a new lesion.
- 2. No FDG-PET at baseline and a positive FDG-PET at follow-up corresponding to a potential new site of disease must have a confirmation by anatomical assessment (e.g., CT, MRI, x-ray) as new site of disease to be considered progressive disease. In such a case, the date of progressive disease will be the date of the initial abnormal FDG-PET.

- e. **Symptomatic deterioration**: Global deterioration of health status requiring discontinuation of **treatment** without objective evidence of progression. Efforts should be made to obtain objective evidence of progression after discontinuation.
- f. Assessment inadequate, objective status unknown. Progression or symptomatic deterioration has not been documented, and one or more target measurable lesions have not been assessed or inconsistent assessment methods were used.

g. Objective status notes:

- 1. Non-measurable and non-target measurable disease do not affect Objective Status in determination of CR (must be absent-a patient who otherwise has a CR, but who has non-measurable or non-target measurable disease present or not assessed, will be classified as having a PR). However, non-measurable and non-target lesions are included in determination of progression (if new sites of disease develop or if unequivocal progression occurs in the opinion of the treating physician).
- 2. An objective status of PR or stable cannot follow one of CR. Stable can follow PR only in the rare case that tumor increases too little to qualify as progression, but enough that a previously documented 30% decrease no longer holds.
- 3. In cases for which initial flare reaction is possible (hypercalcemia, increased bone pain, erythema of skin lesions), objective status is not progression unless either symptoms persist beyond 4 weeks or there is additional evidence of progression.
- 4. Lesions that appear to increase in size due to presence of necrotic tissue will not be considered to have progressed.
- 5. For bone disease documented on bone scan only, increased uptake does not constitute unequivocal progression. However, increase in the soft tissue component of a lesion as measured by CT or MRI would constitute progression.
- Appearance of new pleural effusions does not constitute unequivocal progression unless cytologically proven of neoplastic origin, since some effusions are a toxicity related to therapy or other medical conditions. Increase in the size of an existing effusion does not constitute unequivocal progression, since the fluid status of the patient could alter the size of the effusion.
- 7. If CR determination depends on a lesion for which the status is unclear by the required tests, it is recommended the residual lesion be investigated with biopsy or fine needle aspirate.

10.3 Best Response

This is calculated from the sequence of objective statuses.

a. CR: Two or more objective statuses of CR a minimum of four weeks apart documented before progression or symptomatic deterioration.

- b. PR: Two or more objective statuses of PR or better a minimum of four weeks apart documented before progression or symptomatic deterioration, but not qualifying as CR.
- c. Unconfirmed CR: One objective status of CR documented before progression or symptomatic deterioration but not qualifying as CR or PR.
- d. Unconfirmed PR: One objective status of PR documented before progression or symptomatic deterioration but not qualifying as CR, PR or unconfirmed CR.
- e. Stable/no response: At least one objective status of stable/no response documented at least 6 weeks after registration and before progression or symptomatic deterioration, but not qualifying as anything else above.
- f. Increasing disease: Objective status of progression within 12 weeks of registration, not qualifying as anything else above.
- g. Symptomatic deterioration: Objective status of symptomatic deterioration within 12 weeks of registration, not qualifying as anything else above.

Inadequate assessment, response unknown: Progression or symptomatic deterioration greater than 12 weeks after registration and no other response category applies.

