1.1 Primary Objective

- a. Cohort A To evaluate the pathologic complete response rate (pCR as defined in Section 10.0) in patients with resectable desmoplastic melanoma treated with neoadjuvant pembrolizumab (MK-3475)
- b. Cohort B To evaluate the complete response rate (confirmed and unconfirmed in patients with unresectable desmoplastic melanoma treated with pembrolizumab (MK-3475).

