11.2 Cohort B

a. As a pilot study, Cohort B will use a single stage design with an accrual goal of 21 eligible patients. The anticipated accrual rate for Cohort B is 1 patient per month. Assuming an ineligibility rate of 20%, the study will accrue 26 total patients to enroll 21 eligible patients.

b. Primary Endpoint

The primary endpoint for Cohort B is complete response rate (CR). Given that Cohort B is intended as a pilot trial, we propose single stage design with the assumption that a true CR of 20% or higher indicates that the treatment is of considerable interest for patients with unresectable/metastatic DM whereas a true CR of 5% or lower indicates that the treatment will not be of further interest. Specifically, we will enroll 21 eligible patients with unresectable/metastatic DM. Three or more complete responses out of 21 would be considered evidence that the treatment warrants further study, provided other factors such as toxicity and overall survival also appear favorable. This design has an alpha of 8.5% (i.e. probability of declaring the regimen warrants further study when the true CR is 5%) and a power of 82% (probability of declaring the regimen warrants further study when the true CR is 20%). The higher alpha and lower power used in this design reflect the intention to use this as a pilot trial.

Secondary Endpoints

For the secondary endpoints, 21 eligible patients will be sufficient to estimate the PFS and OS at a particular time point (e.g. 9 weeks) to within ±21.4% (95% confidence interval). However, since PFS is estimated only among patients who do not undergo resection, we will only be able to estimate the PFS to within ±21.9%, ±22.5%, or ±23.9% (95% confidence intervals) if the percentage of patients who undergo resection is 5%, 10%, or 20%, respectively.

d. Translational Medicine Objectives: The statistical analysis of the translational medicine objectives for Cohort B will be the same as for Cohort A except we will use CR as the endpoint instead of pCR.

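### Read literally, Section 10.3 files a PR followed by a single, never-confirmed CR as PR, so Cohort B's primary endpoint (confirmed plus unconfirmed CR) would omit that patient while counting one whose only CR had no earlier PR

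*Combined protocol and SAP*

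**What the plan says.** **Endpoint.** Section 1.1b sets the Cohort B objective: "To evaluate the complete response rate (confirmed and unconfirmed" responses both included. Section 11.2b is shorter: "The primary endpoint for Cohort B is complete response rate (CR"), with no mention of confirmation and no reference to Section 10.3. The decision rule follows: "Three or more complete responses out of 21 would be considered evidence that the treatment warrants further study", subject to toxicity and survival also looking acceptable. The design rates are 5% and 20%, with stated alpha 8.5% and power 82%.

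**Classification.** Section 10.3 derives best response as follows: "This is calculated from the sequence of objective statuses". The items that matter are:

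- 10.3a: "CR: Two or more objective statuses of CR a minimum of four weeks apart documented before progression or symptomatic deterioration".
- 10.3b: "PR: Two or more objective statuses of PR or better a minimum of four weeks apart documented before progression" or symptomatic deterioration, provided the patient is not already a CR under item a.
- 10.3c: "Unconfirmed CR: One objective status of CR documented before progression or symptomatic deterioration but not qualifying as CR or PR".

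**Timing.** Section 7.2c schedules Cohort B disease assessments every 9 weeks for six months and every 4 months after that. Section 10.2g, note 2, rules out PR or stable disease after a CR. It does not rule out PR before one.

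**The concern.** Items b and c rank a confirmed PR above an unconfirmed CR. For an overall response rate this does no harm, because both categories count as responses. For an endpoint meant to include unconfirmed CR it matters: the PR category absorbs some patients who reached CR. Two patients can each have exactly one CR before progression, and the one with the additional earlier PR is the one not counted.

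At stake is the primary count of a 21-patient cohort with a cut-off of three. Section 11.2d also makes CR the responder variable in Cohort B's translational analyses, so the same ambiguity carries into those.

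**Working it through.** **1. Apply 10.3 as written to status sequences on the 9-week schedule.**

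| Sequence | Result under 10.3 | Counted in 1.1b? |
|---|---|---|
| CR (wk 9), progression | Unconfirmed CR | Yes |
| Stable (wk 9), CR (wk 18), progression | Unconfirmed CR | Yes |
| PR (wk 9), CR (wk 18), progression | PR | No |
| PR (wk 9), CR (wk 18), no further scan | PR | No |
| PR (wk 9), CR (wk 18), CR (wk 27) | CR | Yes |
| PR (wk 9), CR (wk 12, unscheduled), progression | Unconfirmed CR | Yes |

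In rows 3 and 4, PR and CR are two statuses of PR or better, 9 weeks apart. Item b is met and item c is therefore closed. Scheduled scans are always more than four weeks apart, so any scheduled PR before a scheduled CR meets the gap. Row 6 escapes only because its gap is three weeks.

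**2. Who is affected.** Because PR or stable cannot follow CR, the next adequate scan after a first CR shows either CR, which confirms it, or progression. The affected patient has had a PR at least four weeks before a single CR, and then progression, symptomatic deterioration, death, withdrawal, resection or the analysis itself comes before any second CR.

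**3. Reproduce the plan's operating characteristics.** With n = 21 and success defined as X ≥ 3:

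P(X ≥ 3 | p) = 1 − [(1−p)^21 + 21·p·(1−p)^20 + 210·p²·(1−p)^19]

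- p = 0.05: 1 − (0.3406 + 0.3764 + 0.1981) = 0.0849. Stated: 8.5%.
- p = 0.20: 1 − (0.0092 + 0.0484 + 0.1211) = 0.8213. Stated: 82%.

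Both agree.

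**4. Sensitivity if 5% and 20% mean any CR.** Let q be the share of patients with any CR who are filed as PR. The documents give no q, so these values are assumptions. The counted rate is p(1−q).

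| q | Counted rate at 20% | Power | Counted rate at 5% | Alpha |
|---|---|---|---|---|
| 0 | 20% | 82.1% | 5% | 8.5% |
| 5% | 19% | 79.1% | 4.75% | 7.5% |
| 10% | 18% | 75.6% | 4.5% | 6.6% |
| 20% | 16% | 67.6% | 4% | 5.0% |

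For scale, a true rate of 20% gives 21 × 0.20 = 4.2 expected complete responders. At q = 10% an average of 0.42 patients would be filed as PR, and at q = 20%, 0.84.

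**5. The other reading of the design rates.** If 5% and 20% were set for CR as 10.3 classifies it, the stated alpha and power stand as printed. Counting every CR would then raise the rates to p/(1−q). At q = 10% (5.6% and 22.2%), alpha would be 10.8% and power 87.7%. At q = 20% (6.25% and 25%), alpha would be 14.0% and power about 93%.

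**The case against.** **The link to 10.3 is inferred.** Neither 1.1b nor 11.2b says the endpoint is read from the best-response table, whereas 11.1b ties Cohort A's endpoint to Section 10.7 by number. An analyst could take confirmed and unconfirmed CR to mean any objective status of CR under 10.2a, and then nothing is lost. This stands in part: the documents do not establish that patients will be dropped. But 10.3 is the only definition of unconfirmed CR, so the literal route leads there, and the two routes can give different primary counts from the same data.

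**The affected group is narrow.** A reader might infer that patients who deepen late from PR to CR are lost in general. The documents do not support that: PR, CR, CR is a confirmed CR. Nor does one unassessable scan drop a patient, because 10.3a does not require consecutive scans, so confirmation is only postponed. Analysis timing matters only if it precedes the next usable scan. All of this stands.

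**The size is assumed.** There is no q in the documents, and 11.2b does not say whether its design rates mean any CR. The figures in step 4 are a range, not evidence of harm. This stands too.

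**Any cut-off makes one patient matter, and the rule is not mechanical.** True: one patient changes the result only at the threshold, Cohort B is a pilot, and toxicity and survival also enter the decision. This lowers the weight of the point but does not remove the inconsistency.

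**Ranking confirmed PR above unconfirmed CR is a coherent convention.** It is, for a best-response table. The difficulty is its use, unqualified, for an endpoint that names unconfirmed CR as a success.

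**Conclusion.** The point holds in a limited form. Under the literal text of 10.3b and 10.3c, a patient with a PR and then, at least four weeks later, a single CR that is never confirmed is not a complete responder, while a patient with one CR and no earlier PR is. Section 11.2b does not settle which count it wants.

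The literal count can never exceed the any-CR count, so the effect is conservative: it can cost a favourable conclusion but cannot create one. If the 5% and 20% rates mean any CR, power falls from 82% to 76% at an assumed q of 10% and to 68% at 20%, and alpha falls from 8.5% to 6.6% and 5.0%.

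A reader might also infer that the stated alpha and power are wrong. They are not; both reproduce exactly. The defect lies in the endpoint definition. Cohort A's pCR endpoint is not involved.

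**What to change.** Add to Section 11.2b: *For the Cohort B primary endpoint, a patient is a complete responder if at least one objective status of CR (Section 10.2a) is recorded before either progression or symptomatic deterioration, whether or not the patient also qualifies as PR under Section 10.3b.* Report confirmed CR (10.3a) beside it, and keep the 10.3 hierarchy for the best-response table.

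State in the same place that the 5% and 20% design rates refer to this any-CR definition, so that the printed alpha and power apply to what is counted. If the sponsor instead intends a PR followed by a single CR to be a non-CR, 1.1b and 11.2b should say so.

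The cost is one or two sentences. Section 10.2 already requires objective status at every evaluation, so no new data, visits or patients are needed.

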10.4 Performance Status

Patients will be graded according to the Zubrod Performance Status Scale.

POINT	DESCRIPTION
0	Fully active, able to carry on all pre-disease performance without restriction.
1	Restricted in physically strenuous activity but ambulatory and able to carry out work of a light or sedentary nature, e.g., light housework, office work.
2	Ambulatory and capable of self-care but unable to carry out any work activities; up and about more than 50% of waking hours.
2	Capable of limited self-care, confined to bed or chair more than 50% of waking hours.
4	Completely disabled; cannot carry on any self-care; totally confined to bed or chair.

10.5 Progression-Free Survival

From date of registration to date of first documentation of progression or symptomatic deterioration (see Section 10.2e), or death due to any cause. Patients last known to be alive without report of progression are censored at date of last contact.

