1.2 Secondary Objectives

Cohort A

- a. To estimate the 9 week response rate (RR) (unconfirmed complete and partial responses) among patients with measurable disease.
- b. To estimate the median overall survival (OS).
- c. To evaluate safety and tolerability of pembrolizumab (MK-3475) in the neoadjuvant setting.

Cohort B

- a. To estimate the median progression-free survival (PFS).
- b. To estimate the median overall survival (OS).
- c. To evaluate safety and tolerability of pembrolizumab (MK-3475) in this setting.
- 1.3 Other objectives (all patients)
 - a. To evaluate the hypothesis that higher mutational load in the patient derived baseline tumor biopsy samples is associated with higher pathologic complete response (pCR).
 - b. To evaluate T cell infiltration into the tumors and circulating tumor DNA profile from blood samples in DM patients and correlate with response to PD-1 blockade.
 - c. To evaluate the clonality of tumor infiltrating T cells in DM patients and correlate with response to PD-1 blockade.
 - d. To evaluate adaptive immune resistant mechanism in DM tumors.

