- If at any time after the first disease assessment the patient's disease is deemed to be unresectable, treatment will continue for 1 more cycle and a repeat disease assessment, using the same techniques as baseline, must be obtained 4 weeks (Day 28 +/- 7 days) later. If, after this second disease assessment the patient's disease is deemed to be resectable the patient must continue with resection as previously planned. Patients who do not undergo a second disease assessment following an initial documentation of progression will be considered failures. [Note: Most responses to pembrolizumab (MK-3475) will occur within 3 cycles, but a delayed response is also possible. If the patient has become unresectable after 3 cycles, one more cycle is given to capture those who might have a delayed response to therapy. If the delayed response is present, unresectable disease may become resectable].

c. Cohort B: Pembrolizumab (MK-3475) for unresectable disease

Patients in Cohort B will receive the following treatment for a maximum of 34 cycles or until the patient has met any of the criteria in Section 7.5, whichever is first.

Agent	Dose	Route	Schedule	
MK-3475 (pembrolizumab)	200 mg	IV over 30 minutes	Day 1, Q 3 weeks	

1 cycle = 21 days.

Pembrolizumab (MK-3475) treatment should be administered after all procedures and assessments have been completed and the patient is deemed eligible. Pembrolizumab (MK-3475) treatment may be administered up to 3 days before or after the protocol-specified Q 3 weeks due to administrative reasons.

Pembrolizumab (MK-3475) treatment will be administered on an outpatient basis.

Pembrolizumab (MK-3475) will be administered as a 30 minute IV infusion. Infusion timing should be as close to 30 minutes as possible; however, a window of -5 minutes and +10 minutes is permitted (*i.e.*, infusion time is 25-40 minutes).

 Disease assessments, using the same technique as baseline, must be performed every 3 cycles (9 weeks) for the first 6 months. Scans should then be obtained every 4 months. Tumor measurements are determined with

scans or if the only site of measurable disease is cutaneous, with photographically measurable disease.

- Patients whose disease becomes resectable in the opinion of the treating investigator, may have surgery which must be performed as described below in Section 7.2. Patient may choose to continue protocol therapy instead of surgical resection.

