- w. Please see Section 15.1 for FEPE submission for translational medicine and Section 15.2 for additional submission of slides for pathology review.
- y. Scans will be obtained every 9 weeks for the first 6 months, then every 4 months.
- * These are the corresponding weeks if there are no dose delays.

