10.6 Time to Death

From date of registration to date of death due to any cause. Patients last known to be alive are censored at date of last contact.

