*NOTE: Upload reports via the Source Documentation: Follow-Up form in Rave®.

f. WITHIN 7 DAYS OF DISCONTINUATION OF PROTOCOL TREATMENT, SUBMIT:

Off Treatment Notice

\$1512 Treatment Form

\$1512 Adverse Event Form.

g. WITHIN 14 DAYS OF PROGRESSION OR RELAPSE, SUBMIT:

Follow-Up Tumor Assessment Form (RECIST 1.1) OR Follow-Up Form (if patient underwent surgery to resect disease after starting protocol therapy).

Radiology reports from all scans performed to assess disease*. Physician must note tumor measurement in patient records.

Physician report documenting any measurements of skin lesions made during a physical examination.*

If patient was on protocol treatment at the time of progression, also submit the materials specified in Section 14.4f.

See Section 15.0 for specimen submission requirements.

*NOTE: Upload reports via the Source Documentation: Follow-Up form in Rave®.

h. WITHIN 14 DAYS OF SURGERY TO RESECT DISEASE, SUBMIT:

S1512 Pathologic Response Form

All operative and pathology reports from the procedure*.

Submit surgical specimen and specimen from biopsy between Weeks 3-5. See Section 15.0 for specimen submission requirements.

*NOTE: Upload reports via the Source Documentation: Follow-Up form in Rave®.

i. ONCE OFF ALL PROTOCOL TREATMENT SUBMIT EVERY 6 MONTHS FOR THE FIRST 2 YEARS, THEN YEARLY FOR A TOTAL OF 5 YEARS FROM INITIAL REGISTRATION:

Follow-Up Form

Late Effects Form (if prior to treatment for progression or relapse or a second primary, and prior to non-protocol treatment, the patient experiences any severe [Grade \geq 3] long term toxicity that has not been previously reported).

j. WITHIN 28 DAYS OF KNOWLEDGE OF DEATH:

Notice of Death **and all of the items listed in Section 14.4e** (if the patient was still on protocol treatment) or Follow-Up Form (if the patient was off protocol treatment) documenting death information.

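### Cohort B PFS is censored at last contact rather than last disease assessment, so it can be overstated when contact continues after scans stop

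*Combined protocol and SAP*

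**What the plan says.** Median PFS is a secondary objective of Cohort B only (Section 1.2). Section 10.5 runs it "From date of registration to date of first documentation of progression or symptomatic deterioration", or death from any cause, and adds: "Patients last known to be alive without report of progression are censored at date of last contact". Section 10.6 uses the same kind of rule for survival: "Patients last known to be alive are censored at date of last contact".

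Contacts and scans follow different clocks in Cohort B:

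- **Contacts.** Dosing visits are every 3 weeks (Section 7.2c). After treatment there are visits at 6 weeks, then every 12 weeks, then every 6 months to year 5 (Section 9.2, footnote c). Follow-up forms are due as follows: "ONCE OFF ALL PROTOCOL TREATMENT SUBMIT EVERY 6 MONTHS FOR THE FIRST 2 YEARS, THEN YEARLY FOR A TOTAL OF 5 YEARS" (Section 14.4i).
- **Scans.** Section 9.2, footnote y: "Scans will be obtained every 9 weeks for the first 6 months, then every 4 months". Section 7.2c agrees after month 6: "Scans should then be obtained every 4 months". Footnote k of the same calendar instead has assessments every 9 weeks until progression.

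Section 10.2f has a category for inadequate assessment with unknown status, but Section 10.5 does not use it. No section gives a PFS rule for missed scans.

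**The concern.** Last contact suits survival, because any contact establishes that the patient is alive. It does not suit PFS, because a contact without an assessment leaves progression status unknown. A Cohort B patient who stops scans because of toxicity, refusal or care elsewhere, but is still known to be alive, stays in the risk set as event-free. That pushes the Kaplan-Meier curve upward.

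There is no control arm in which the same bias could cancel. The planned confidence interval covers sampling error only. At stake is the credibility of the Cohort B PFS estimate, not the decision rule for the cohort.

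**Working it through.** **1. The plan's own precision.** The worst-case 95% half-width is 1.96 × √(0.25/n).

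- n = 21: 21.4 points.
- 5%, 10% or 20% resected and excluded, so n = 19.95, 18.9 or 16.8: 21.9, 22.5 or 23.9 points.

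All four match Section 11.2. The CR rule of at least 3 of 21 also reproduces: alpha 8.5%, power 82%. The censoring rule enters none of these figures.

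**2. Simulation of the two rules.** Each scenario has 40,000 simulated patients, each censored both ways.

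From the documents: both scan schedules, contact every 3 weeks, and 26 months of accrual (26 patients at 1 per month).

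Assumed, because the documents are silent:

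- exponential progression with median 6, 12 or 24 months;
- median survival after progression of 18 months;
- 12 months of follow-up after accrual;
- scans within ±1 week of schedule;
- 0% to 30% of patients stopping scans at a random time in year 1 while staying in contact;
- no clinical detection of progression after scans stop.

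24-month PFS (%) on the schedule of 9 weeks then 4 months, shown as last contact / last assessment / complete scanning:

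| Stop scans | True median 6 months | 12 months | 24 months |
|---|---|---|---|
| 0% | 7.5 / 6.4 / 7.5 | 27.4 / 25.2 / 27.4 | 52.0 / 49.8 / 52.0 |
| 10% | 10.7 / 6.7 / 7.5 | 30.5 / 24.7 / 27.1 | 54.5 / 49.2 / 52.3 |
| 20% | 14.0 / 6.9 / 7.5 | 33.7 / 24.3 / 27.2 | 57.0 / 48.6 / 52.4 |
| 30% | 17.3 / 7.2 / 7.6 | 36.9 / 23.8 / 27.4 | 59.1 / 47.2 / 52.0 |

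- **Gap between rules, full adherence:** 1.1 to 2.2 points here, and under 1 point on the schedule of every 9 weeks until progression. The assumed progression-free probability at 24 months is 2^(−24/median), that is 6.25%, 25% and 50%. Last contact is 1.25, 2.4 and 2.0 points above these, and last assessment is within 0.2. Part of the excess is the usual delay from dating progression at a scan.
- **Gap between rules, 10% to 30% lapse:** from 3.4 points (10.2 − 6.8; median 6, 10% lapse, 9-week schedule) to 13.1 points (36.9 − 23.8; median 12, 30% lapse, table above).
- **Last contact against complete scanning, table above:** from 2.2 points (54.5 − 52.3) to 9.7 points (17.3 − 7.6). The rest of the gap between rules arises because last-assessment censoring runs somewhat low.

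**3. The median.** At 20% lapse in the same simulation, the medians under last contact and last assessment are 10.0 and 6.4, 14.4 and 14.2, and 30.1 and 22.4 months, for true medians of 6, 12 and 24. Complete scanning gives 6.4, 14.2 and 26.2. The pattern is uneven because documented progressions fall on scan dates: 27 weeks is 6.2 months, and the next scan is at 10.2. A true median of 6 sits just below a 4-month gap, so a small change in the curve moves the estimate across it. With scans exactly on schedule and a true median of 8 or 12 months, both rules give the same median at 20% lapse.

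**4. Long follow-up.** With a 5-year cut, true median 6 and 20% stopping scans between months 2 and 9, 12.5-month PFS is 35.3% under last contact, 34.3% under last assessment and 30.4% with complete scanning. Changing the censoring date alone removes (35.3 − 34.3)/(35.3 − 30.4) = 1.0/4.9, about a fifth, of the bias. By then most unscanned patients have died, and the death is counted as an event long after the unseen progression. Under the same assumptions the median is 9.2 months under the plan, 8.9 with the censoring change alone, and 6.2 when events after two or more missed assessments are also censored.

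**5. Clinical detection.** If progression in patients off scans is found clinically at about 3 months, the excess in 12.5-month PFS falls from about 2 to 8 points to about 0.5 to 2 points.

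**The case against.** The strongest defence is that a contact is not empty of information. Censoring requires that no progression has been reported. Visits before progression include history, physical and skin examination as well as CT (Section 9.2). Lesions can be measured with calipers (Section 10.1), and a new lesion or unequivocal progression of non-measurable disease in the physician's opinion counts as progression (Section 10.2d). Symptomatic deterioration and death are events. Tumour forms are due until progression, and progression must be reported within 14 days (Section 14.4). This stands, and it is why the larger figures apply only where progression goes undetected after scans stop.

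A reader might infer from "whole body scanning at specific intervals is necessary to determine that progression is NOT present" in Section 10.2 that only scans can show absence of progression. The sentence goes on to limit itself to disease outside the target areas. It is a rule about anatomical coverage and does not say that other contacts are uninformative.

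A reader might also infer that Cohort B median PFS will be overstated by months. The documents do not support that. They give no missed-scan rate and no expected PFS, and the multi-month shifts depend on where the true median falls relative to the scan dates.

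Nor is last-assessment censoring neutral. If progressions found off schedule are still counted as events while patients without them are censored back at the last scan, it runs low. That affects the fix, but it does not justify crediting unassessed time as progression-free.

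**Conclusion.** The point holds as a conditional one. Section 10.5 applies a survival-type censoring rule to PFS, nothing elsewhere overrides it, and the bias from missed scans is upward.

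Under the assumptions above, the two rules differ in 24-month PFS by about 1 to 2 points with full adherence on the sparser scan schedule. They differ by about 3 to 13 points if 10% to 30% of patients stop scans, stay in contact and have no clinical detection. With prompt clinical reporting the difference is much smaller. Fixed-time PFS shows the effect more reliably than the median.

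PFS is a descriptive secondary endpoint in a 21-patient pilot cohort with stated precision of ±21.4 to ±23.9 points. The primary CR rule, its alpha and power, and Cohort A are unaffected. The change is worth making because it is cheap and the bias is in one direction.

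**What to change.** 1. In Section 10.5, censor patients who are alive without documented progression or symptomatic deterioration at the last adequate disease assessment (one not classed as inadequate under Section 10.2f), or at registration if there is none.
2. Add a sensitivity analysis that censors events occurring after two or more missed assessments at the last adequate assessment before the gap. At long follow-up this removes most of the bias.
3. Keep last-contact censoring as a further sensitivity analysis, because last-assessment censoring can run low when off-scan progression is still reported.
4. Leave Section 10.6 unchanged.
5. Reconcile Section 9.2 footnote k with footnote y and Section 7.2c. After month 6, two missed assessments span 2 × 9 = 18 weeks on one reading and 2 × 4 = 8 months on the other.

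The cost is one sentence, two sensitivity runs and one reconciliation. Assessment dates are already collected on the tumour assessment forms. The downside is that PFS may look slightly less favourable.
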